9.1 Confidentiality

Information about study Participants will be kept confidential and managed according to the requirements of the Health Insurance Portability and Accountability Act of 1996 (HIPAA). Those regulations require a signed Participant authorization informing the Participant of the following:

- What protected health information (PHI) will be collected from Participants in this study
- Who will have access to that information and why
- Who will use or disclose that information
- The rights of a research Participant to revoke their authorization for use of their PHI.

In the event that a Participant revokes authorization to collect or use PHI, the investigator, by regulation, retains the ability to use all information collected prior to the revocation of

Participant authorization. For Participants that have revoked authorization to collect or use PHI, attempts should be made to obtain permission to collect at least vital status (long term survival status that the Participant is alive) at the end of their scheduled study period.

9.2 Source Documents

Source data comprise all information, original records of clinical findings, observations, or other activities in a clinical trial necessary for the reconstruction and evaluation of the trial. Source data are contained in source documents. Examples of these original documents, and data records include: hospital records, clinical and office charts, laboratory notes, memoranda, Participants' diaries or evaluation checklists, pharmacy dispensing records, recorded data from automated instruments, copies or transcriptions certified after verification as being accurate and complete, microfiches, photographic negatives, microfilm or magnetic media, x-rays, Participant files, and records kept at the pharmacy, at the laboratories, and at medico-technical departments involved in the clinical trial. When applicable, information recorded on the CRF shall match the Source Data recorded on the Source Documents.

All clinical notes and discussions regarding the patient will be appropriately captured, signed and documented.

9.3 Case Report Forms

An eligibility form will be completed for each Participant enrolled into the clinical study. As needed, an adverse event worksheet will be completed for study Participants experiencing AEs. The site investigator or designated study staff will review, approve, and sign/date each completed CRF; the signature serving as attestation that all clinical and laboratory data entered on the CRF are complete, accurate, and authentic. Data will be entered into an excel database.

9.4 Data Management

- a) Data is entered into an excel spreadsheet
- b) Study data will be reviewed regularly by the Investigator and Study Coordinator for the following:
 - a. Participant inclusion criteria has been met
 - b. Transcription of data is accurate and complete
 - c. Units of measure are recorded appropriately
- c) Details of the study treatments including treatment parameters, such as percent of MT for each treatment, will be retained within the TMS device by the TrakStar software. In addition, a daily summary of the treatment will be created and stored in the Participant's source document.
- d) Case files will be created for each Participant where completed visit CRFs will be stored. Any adverse event CRFs will also be stored in the case file.

9.5 Data Security and Confidentiality

- a) Non-electronic source document data will be stored in a locked cabinet in a secure office. Only authorized study staff will have access.
- b) Electronic data will be stored on a secure database. Only authorized users will have access. All users will have unique identifiers and passwords. Sharing of log-in information is not permitted.

9.6 Records Retention

The sponsor-investigator will maintain records and essential documents related to the conduct of the study. These will include Participant case histories and regulatory documents.

The sponsor-investigator will retain the specified records and reports for:

1. Up to 2 years after the marketing application is approved for the drug; or, if a marketing application is not submitted or approved for the drug, until 2 years after shipment and delivery of the drug for investigational use is discontinued and the FDA has been so notified. OR
2. As outlined in the Mayo Clinic Research Policy Manual –“Retention of and Access to Research Data Policy” [REDACTED], whichever is longer.

10 Study Monitoring, Auditing, and Inspecting

10.1 Study Monitoring Plan

This study will be monitored by the Mayo Clinic Office of Research Regulatory in accordance with standard operating procedures.

10.2 Auditing and Inspecting

The sponsor-investigator will permit study-related monitoring, audits, and inspections by the IRB, the monitor, and government regulatory agencies, of all study related documents (e.g., source documents, regulatory documents, data collection instruments, study data etc.). The sponsor-investigator will ensure the capability for inspections of applicable study-related facilities (e.g., pharmacy, diagnostic laboratory, etc.).

Participation as a sponsor-investigator in this study implies acceptance of potential inspection by government regulatory authorities and applicable compliance offices.

11 Ethical Considerations

This study is to be conducted according to United States government regulations and Institutional research policies and procedures.

Although this study is considered more than minimal risk to adolescents, TMS treatments (1 Hz, 10 Hz, cTBS, and iTBS) offer a potential direct benefit for the individual Participant. In addition, the schedule of mood assessments and daily assessment during the interventional portion of the study for any adverse events has been developed for the purpose of monitoring the Participant's well-being.

This protocol and any amendments will be submitted to a properly constituted local IRB, in agreement with local legal prescriptions, for formal approval of the study at each participating site. The decision of the IRB concerning the conduct of the study at MUSC will be documented in writing to the regulatory sponsor before commencement of this study.

All families and Participants for this study will be provided a consent/assent form describing this study and providing sufficient information for Participants to make an informed decision about their participation in this study. This consent/assent form will be submitted with the protocol for review and approval by the site IRB for the study. The formal consent of a Participant, using the approved IRB consent/assent form, must be obtained before that Participant undergoes any study procedure. This form must be signed and dated by the Participant, the Participant's legally-authorized representative, and the individual obtaining informed consent/assent.

12 Study Finances

12.1 Funding Source

The study will be funded by a National Institute of Mental Health Grant 1R01MH113700. Neuronetics, Inc. will provide grant-in-kind support for NeuroStar magnetic stimulators and disposable SenStar Shields.

88. Research USDoHaHSFaDACfDaRHCFBEa. Design Considerations for Pivotal Clinical Investigations for Medical Devices Guidance for Industry, Clinical Investigators, Institutional Review Boards, and Food and Drug Administration Staff. 2013. Accessed October 8, 2016.
89. *PASS 14 Power Analysis and Sample Size Software* [computer program]. Kaysville, Utah, USA: NCSS, LLC.; 2016.

15. Appendix A Concomitant Medication List

CONCOMITANT MEDICATION LIST

This list should not be considered exhaustive. Drugs that are categorized into one of the drug categories listed in the table below will be treated similarly.

| CLASS: Drug | PRN | Chronic |
|---|-----|--------------------------|
| ANTIASTHMA DRUGS | | |
| Theo-Dur (theophylline) | N | N |
| Bronchodilators | | |
| Alupent (metaproterenol), Proventil (albuterol), Ventolin (albuterol) | Y | Y |
| Steroids | | |
| Inhaled (Beclovent [beclomethasone], Azmacort [triamcinolone], Vanceril [beclomethasone]) | Y | Y |
| Oral | Y | Y |
| Leukotriene antagonists | | |
| Accolate (zafirlukast), Zyflo (zileuton), Singulair (monoleukast) | N | Y |
| ANTICOAGULANTS | | |
| Coumadin (warfarin) | N | Y (w/ stable protime) |
| ANTICHOLINERGICS | | |
| Cogentin (benztropine), Artane (trihexyphenidyl), etc. | N | N |
| Phenylpropanolamine (PPA) and pseudoephedrine | N | N |
| ANTI-HISTAMINE and DECONGESTANTS | | |
| Sedating | | |
| Anticholinergic (Benadryl [diphenhydramine], chlorpheniramine, brompheniramine, Atarax [hydroxyzine]) (not for psychiatric indications) | N | N |
| Non-sedating | | |
| Allegra (fexofenadine), Claritin (loratadine), Zyrtec (cetirizine) | Y | Y |
| Hismanal (astemizole) | N | N |
| ANTI-INFECTIVE AGENTS | | |
| Antibacterial antibiotics (Penicillin, sulfa, etc.) | Y | Y |
| Antifungal agents (ketoconazole, fluconazole, etc.) | | |
| Topical creams and ointments | Y | Y |
| Oral antifungals (single-dose for vaginitis OK) | Y | N |
| Antiviral agents | | |
| Zovirax (acyclovir), Famvir (famcyclovir), Valtrex (valacyclovir) | Y | Y |
| Antiretroviral drugs (e.g. AZT, protease inhibitors) | N | N |
| ANTI-NEOPLASTIC AGENTS | | |
| SKELETAL MUSCLE RELAXANTS | | |
| Lioresal (baclofen), Flexeril (cyclobenzaprine), Parafon Forte (chlorzoxazone), Robaxin (methocarbamol), Soma (carisoprodol) | N | N |

| CLASS: Drug | PRN | Chronic |
|--|-----|---------|
| ANALGESICS AND ANTIPYRETICS | | |
| Nonsteroidal anti-inflammatory agents (aspirin, ibuprofen, naproxen) | Y | Y |
| Opiate Agonists / Partial Agonists (including Ultram [tramadol]) | N | N |
| Miscellaneous analgesics & antipyretics (acetaminophen, paracetamol) | Y | Y |
| CARDIOVASCULAR DRUGS (All drugs in this category must be stable for at least 3 months) | | |
| CARDIAC DRUGS | | |
| Calcium Channel Blockers for coronary disease or angina (see also "Antihypertensives") (Calan [verapamil], Cardizem [diltiazem], Norvasc [amlodipine], Procardia [nifedipine]) | N | Y |
| Antiarrhythmics | | |
| Cordarone (amiodarone), lidocaine (note: local anesthesia injection OK), Mexilit (mexiletine), Norpace (disopyramide), Procan (procainamide), quinidine, Tambocor (flecainide) | N | N |
| Digoxin (blood levels must be monitored) | N | Y |
| ANTI-HYPERTENSIVE AGENTS (All anti-hypertensives must be stable dose x 1 month) | | |
| ACE Inhibitors (Vasotec, Capoten, Zestril) | N | Y |
| Angiotensin receptor blockers (Cozaar) | N | Y |
| Calcium Channel Blockers | N | Y |
| Diuretics | Y | Y |
| Phentolamine | N | N |
| Beta-Adrenergic Blockers (see also Anti-Migraine) | | |
| Low lipid solubility/CNS penetration (Corgard [nadolol], Tenormin [atenolol]) | Y | Y |
| High lipid solubility/CNS penetration (Inderal [propranolol], Lopressor [metaproterenol]), (low lipid solubility preferred) | Y | Y |
| Peripherally-acting alpha adrenergic agents | | |
| Cardura (doxazosin), Hytrin (terazosin), Minipress (prazosin) | Y | Y |
| Centrally-acting alpha adrenergic agents | | |
| Aldomet (methyldopa), Catapres (clonidine) | N | N |
| All others (guanethidine, reserpine, etc.) | N | N |
| ANTILIPEMIC AGENTS | | |
| Niacin (no slow-release preparations), Lipitor (atorvastatin), Lopid (gemfibrozil), Mevacor (lovastatin), Zocor (simvastatin) | N | Y |
| VASODILATING AGENTS | | |
| Hydralazine | N | Y |
| minoxidil (topical OK) | N | C |
| ANTI-CONVULSANTS | | |
| | N | N |

| CLASS: | Drug | PRN | Chronic |
|---|--|-----|---------|
| PSYCHOTHERAPEUTIC AGENTS | | | |
| | Antidementia drugs (donepezil, etc.), Antidepressants, Antipsychotics (Thorazine, Prolixin, etc.), Miscellaneous Psychotherapeutic Agents | N | N |
| | Anxiolytics (per protocol) | Y | N |
| | Stimulants | N | |
| | Sedatives and Hypnotics | | |
| | Barbiturates, Benzodiazepines (except those allowed per the protocol), Other hypnotic agents | N | N |
| | Ambien (zolpidem; per protocol), chloral hydrate (per protocol), Sonata (zaleplon; per protocol), Lunesta (eszopiclone; per protocol), Rozerem (ramelteon; per protocol) | Y | N |
| ANTIMANIC AGENTS | | | |
| | Anticonvulsants, lithium | N | N |
| HORMONES & SYNTHETIC SUBSTITUTES | | | |
| | Corticosteroids (methylprednisolone, prednisone) | Y | N |
| | Mineralocorticoids (Florinef [fludrocortisone]) | N | N |
| | Topical steroids (creams, ointments, eyedrops) | Y | Y |
| | pregnenolone | N | N |
| | Androgens | N | N |
| | DHEA, testosterone, danazol | N | N |
| | Contraceptives | | |
| | Hormonal (dose must be stable for at least 3 months): Oral, Vaginal Ring, Patch, Injections, Norplant (levonorgestrel) | N | Y |
| | Intrauterine device | Y | Y |
| | Latex condom, diaphragm and or cervical cap with spermicide | Y | Y |
| | Estrogen replacement (postmenopausal, stable dose for ≥3 months) | N | Y |
| | Thyroid (stable dose for ≥3 months and thyroid function tests within normal limits. Clinical significance to be determined by the physician) | N | Y |
| ANTIDIABETIC AGENTS | | | |
| | Oral hypoglycemic agents | N | Y |
| | Insulin's | Y | Y |
| DERMATOLOGIC AGENTS | | | |
| | Topical steroid preparations, Rogaine (topical minoxidil), Miscellaneous creams, ointments, etc. | Y | Y |
| VITAMINS | | Y | Y |
| OVER-THE-COUNTER SUPPLEMENTS | | | |
| | chromium picolinate, DHEA, melatonin, pregnenolone, St. John's Wort | N | N |

| CLASS: | Drug | PRN | Chronic |
|---|---|------------|----------------|
| GASTROINTESTINAL DRUGS | | | |
| | Cisapride (propulsid) | Y | Y |
| Antiemetics | | | |
| | Over-the-counter (e.g., Emetrol [dextrose], Coke syrup) | Y | Y |
| | Phenothiazines & related drugs (Compazine [prochloroperazine], Phenergan [promethazine], Reglan [metoclopramide], Tigan [trimethobenzamide]), Anzemet (dolasetron), Kytril (granisetron), Zofran (ondansetron) | Y | N |
| | Marinol (dronabinol), | N | N |
| Antacids | | | |
| | AlternaGel (aluminum hydroxide), Amphojel (aluminum hydroxide), Basaljel (aluminum carbonate), Bicitra (sodium citrate), Maalox (calcium carbonate), MagOX (magnesium oxide), Mylanta (magnesium hydroxide), Tums (calcium carbonate), UroMag (magnesium oxide) | Y | Y |
| Antidiarrhea agents | | | |
| | Arco-Lase (trizyme), Furoxone (furazolidone), Motofen (difenoxylin), Sandostatin (octreotide acetate) | N | N |
| | Imodium (loperamide), Lomotil (diphenoxylate), Pepto-Bismol (bismuth subsalicylate) | Y | N |
| Cathartics & Laxatives | | | |
| | Colace (docusate), enemas, Metamucil, Perdiem, Senokot, Soflax, Unifibre | Y | Y |
| | Dialose (docusate) | Y | Y |
| Antisecretory agents | | | |
| | H2 Blockers | N | N |
| | Axid (nizatidine), Pepcid (famotidine), Zantac (ranitidine) | Y | Y |
| Proton pump inhibitors | | | |
| | Prevacid (lansoprazole), Prilosec (omeprazole) | Y | Y |
| Miscellaneous gastrointestinal drugs | | | |
| | Carafate (sucralfate) | Y | Y |
| | Reglan (metoclopramide) | N | N |
| | Levsin (L-hyoscyamine sulfate) | Y | Y |
| ANTI-MIGRAINE | | | |
| | DHE 45 (dihydroergotamine), Imitrex (sumatriptan), methysergide, Midrin (isometheptene mucate), Zomig (zolmitriptan) | N | Y |
| | Fiorinal (butalbital, ASA, caffeine), Cafergot (ergotamine) | Y | Y |
| | Nonsteroidal anti-inflammatory drugs (ibuprofen, naproxen, Toradol, etc.) | Y | Y |
| Beta-blocking drugs | | | |
| | Corgard (nadolol), Tenormin (atenolol), Other beta-blockers (e.g., Inderal [propranolol]) | Y | Y |
| SKIN & MUCOUS MEMBRANE AGENTS | | Y | Y |

| CLASS: | Drug | PRN | Chronic |
|--|--|------------|----------------|
| MISCELLANEOUS DRUGS | | | |
| | Accutane, All over-the-counter diet pills, Ionamin (phentermine resin), Lioresal (baclofen), Wellbutrin (bupropion), Zyban (bupropion) | N | N |
| | Allopurinol, colchicine | Y | Y |
| | Fosamax (alendronate) | N | Y |
| | Gold compounds, hydroxychloroquine, and methotrexate for severe arthritis | N | Y |
| | Smoking cessation aids (Nicorette, nicotine patches) | Y | Y |
| | Chantix (varenicline) | N | N |
| ENDNOTES | | | |
| N = Never to be used in this study. Y = Can be used in this study for either PRN or Chronic use as indicated in the table. | | | |
| C = Call for Sponsor approval. Approval for these medications is generally granted if the patient is otherwise acceptable, including stable medical condition, no undue risk, no other "marginal" considerations in the medical history or concomitant medications. Or may be used during the long-term maintenance phase with certain restrictions. | | | |

16 Appendix B ICF and TMS Measures

Collection of ICF and TMS Neurophysiology Measures

- 1) The subject is greeted and seated comfortably.
- 2) Details of the subject's session will be recorded in the study file.
- 3) Subjects, technicians, and the study physician (who will always be present) will be provided with earplugs, which are to be worn at all times. Subjects will be instructed to turn off all cell phones and pagers. Eyeglasses will be removed. Subjects should not have any metal above their neckline (with the exception of orthodontics), specifically hairpins or large metallic earrings. Subjects will be instructed to sit quietly with their eyes open throughout the measurements.
- 4) The TMS coil will be wiped with an alcohol swab before and after each session.
- 5) EMG set up includes a 1k gain, HPF 30, and LPF 500 or 1000. When the operator is doing calibration setting, the isolated bioamp must be on the lowest setting. When collecting data the operator must ensure that the switch of the bioelectric amplifier is on.

Connecting EMG Leads:

- a. EMG leads are connected to the right hand.
- b. The white wire goes in the red circle.
- c. The black wire goes in the green circle.
- d. The green wire goes in the white circle (this is the ground).
- e. Place one electrode on abductor pollicis brevis (white wire).
- f. Place one lead on the middle joint of the index finger (black wire).
- g. Place ground lead on the hand that you are measuring (green wire).
- h. On the computer, the red line refers to the right hand.

- 6) At the start of each session, the operator must check the plastic casing of the stimulating coil for any signs of external damage. If any cracks are visible in the housing, the stimulating coil must not be used and should be serviced.
- 7) Connect the coil to the main Magstim unit. Switch on, select the desired stimulating power by using the output power knob, and press the run switch on the front panel of the Magstim to arm the unit. The Magstim will charge and the “ready” display will be illuminated.
- 8) Position the stimulating coil on the desired area to be stimulated. Press and hold down one or both of the safety switches at the baseline of the stimulating coil. Triggering the Magstim results in a magnetic pulse being delivered by the stimulating coil, stimulating the nerves beneath it.
- 9) When necessary, reposition the stimulating coil and/or modify the stimulating power level to suit the requirements for the next stimulus. Meanwhile, the Magstim will have recharged and can be triggered once again in the normal manner.
- 10) When the tests have been completed, press the “stop” switch on the front panel of the Magstim and replace the stimulating coil on the coil hanger. The Magstim will then revert to standby mode and cannot be triggered until it is armed once more.
- 11) The TMS coil is held tangential to the subject’s head at 45 degrees.
- 12) Single-pulse measures (MT and CSP):
 - a. When giving pulses, always wait 5-10 seconds between pulses.
 - b. Start at 30% intensity and administer a few pulses to acclimate the subject to the test conditions.
 - c. Increase to 40% intensity and then by 10 at a time to get motor responses, and then decrease intensity.
 - d. Administer 10 successive pulses at each intensity. If 6 of 10 pulses are not sufficient, this is the threshold point. If 5 of 10 pulses elicit a motor response, decrease the intensity until 6 of 10 do not elicit a motor response.
 - e. Measure optimal site laterally and posterior from the vertex.
 - f. Single-pulse measures are performed with submaximal, tonic, hand muscle contraction. This reduces variability in the CSP (Mathis et al. 1998, Bajbouj et al. 2006).
 - g. The duration of the CSP is measured from the onset of the corticospinal mediated EMG response, to the end of the silent period. The end is the point at which averaged tonic EMG activity reaches the amplitude of mean EMG activity prior to TMS.
- 13) Paired-pulse measures (ICI and ICF):
 - a. The figure of eight coil and the bistim module are utilized for these measurements.
 - b. Two stimulations are given in succession, as described previously (Kujirai et al. 1993, Nahas et al. 2007). The first pulse is the conditioning stimulus. The second pulse is the test pulse.
 - c. Stimulations for ICI are spaced 1-5 msec apart, and 100-200 msec apart.
 - d. Stimulations for ICF are spaced 7-20 msec apart.
 - e. Complete 10 trials of the test stimuli, each administered 10 seconds apart. Peak to peak amplitudes of the conditioned response are averaged and expressed as a percentage of the average of the test response amplitudes.

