Collection of ICF and TMS neurophysiology measures: TMS data will be collected with standard procedures published previously.⁶⁵ Participants are seated in a comfortable chair during the procedure. All participants and research team members wear ear plugs during testing sessions. Surface electromyography (EMG) readings are recorded from the abductor pollicis brevis (APB) muscle. The research team will ensure participants maintain relaxation during the procedures with audio feedback tests. TMS stimulation will be applied to the hand area of the contralateral cortex with a figure-of-eight magnetic coil (with a coil diameter of 70 mm on each loop) using the Magstim 200 magnetic stimulator device. The TMS coil is held tangentially on the head with the handle backward at 45 degrees laterally from the midline to determine resting motor threshold. The optimal coil position is located by moving the coil in 1-cm increments over the motor cortex. The resting motor threshold (RMT) is defined as the stimulation intensity which elicits a motor evoked potential (MEP) of > 50 microvolts in 5 of 10 trials with a relaxed APB muscle. For ICF measurements, a subthreshold conditioning stimulus (CS) which is set to 80% of RMT precedes a suprathreshold test stimulus (TS), which is calibrated to produce an average MEP of 0.5 to 1.5 millivolt peak-to-peak amplitude in the contralateral APB muscle. Conditioning stimuli are delivered to the motor cortex prior to the TS in one of five random interstimulus intervals (ISIs): 2 msec, 4 msec for ICI; 10 msec, 15 msec, and 20 msec for ICF. Changes in TS MEP amplitude of each ISI are expressed as a percentage of the mean unconditioned MEP amplitude. Administration of tests is counterbalanced to prevent order effects. Please see Section 16, Appendix B for detailed methodology for collection of ICF and TMS neurophysiology measures.

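### Appendix B's motor-threshold procedure does not match the resting threshold in Section 5.2 that sets the ICF conditioning stimulus

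*Combined protocol and SAP*

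**What the plan says.** Section 5.2, under the collection of ICF and TMS neurophysiology measures, defines resting motor threshold (RMT) as the intensity that elicits a "motor evoked potential (MEP) of > 50 microvolts in 5 of 10 trials with a relaxed APB muscle". On muscle state it adds: "The research team will ensure participants maintain relaxation during the procedures with audio feedback tests". The ICF measurement then uses "a subthreshold conditioning stimulus (CS) which is set to 80% of RMT", followed by a test stimulus calibrated to an average response of 0.5 to 1.5 millivolts. The paragraph ends by sending the reader to Appendix B for the detailed methodology.

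In Appendix B, item 12 has a heading that opens "Single-pulse measures (MT and CSP", so motor threshold and cortical silent period (CSP) share one set of instructions. Item 12d says: "If 6 of 10 pulses are not sufficient, this is the threshold point". It continues: "If 5 of 10 pulses elicit a motor response, decrease the intensity until 6 of 10 do not elicit a motor response". Item 12f says: "Single-pulse measures are performed with submaximal, tonic, hand muscle contraction". The reason given for 12f is lower variability in the CSP. Item 12 has no separate resting condition for motor threshold.

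**The concern.** Section 5.2 makes Appendix B the working procedure, yet the two differ on whether the muscle is relaxed or contracted and, on a literal reading, on how many responses define threshold. An operator who follows Appendix B as written records a threshold that is not the RMT of Section 5.2. If that value is then used as the RMT, the ICF conditioning pulse is set from the wrong quantity.

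ICF enters the trial in several places:

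- Baseline ICF, cut at 1.5, fixes the Phase I stratum (Sections 3.1, 5.3 and 6.2). The same high/low status is the moderator in the treatment-by-biomarker test of the primary aim (Section 7.2).
- ICF over the six weeks, measured weekly, is the secondary endpoint (Section 3.3, Table 3).
- A separate ICF, taken at the baseline of the extension trial, decides between cTBS and iTBS in Phase II (Sections 3.1 and 5.3).

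The definition of threshold should therefore be the same wherever it is written and at every visit.

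**Working it through.** The plan has no sample-size or power figure to reproduce on this point. The check is a comparison of texts with a small amount of arithmetic.

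**1. The two rules side by side**

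| Feature | Section 5.2 | Appendix B, item 12 |
|---|---|---|
| Measure named | Resting motor threshold | MT, together with CSP |
| Muscle state | Relaxed, checked by audio feedback | Submaximal tonic contraction (12f) |
| Size of a response | Above 50 microvolts | Not stated in 12d |
| Response count at threshold | 5 of 10 | 6 of 10 fail, so 10 − 6 = 4 of 10 respond (12d) |
| Action at exactly 5 of 10 | Threshold reached | Lower the intensity |

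**2. Does anything else in Appendix B settle it?** No. Item 3 asks participants to sit quietly with eyes open, which does not address hand contraction. Item 13, on paired pulses, gives neither a conditioning intensity nor a muscle state.

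**3. How the threshold reaches ICF.** Conditioning intensity = 0.80 × threshold. With T1 the Section 5.2 threshold and T2 the Appendix B threshold, the ratio of conditioning intensities is 0.80·T2 / 0.80·T1 = T2/T1, so any relative difference passes through in full. The documents do not give T2/T1, nor how ICF responds to it.

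**4. What the threshold does not reach.** The ICF test stimulus is set by response amplitude, not as a multiple of threshold. For treatment intensity, Section 5.3 has motor threshold determined by the NeuroStar User Manual procedure, so the conflict does not extend to rTMS dosing.

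**5. How often the two counts would part company.** Assume independent pulses with response probability p at the intensity being tested; p is not in the documents. Let X be the number of responses in 10.

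- p = 0.5: P(X = 5) = 252/1024 = 0.246. Here Section 5.2 stops and 12d lowers the intensity.
- p = 0.5: P(X ≥ 5) = 638/1024 = 0.623. Here the 6-failure point of 12d has not been reached.
- p = 0.4: P(X = 5) = 0.201 and P(X ≥ 5) = 0.367.
- p = 0.6: P(X = 5) = 0.201 and P(X ≥ 5) = 0.834.

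The difference in counts, if meant literally, would therefore arise often in practice. These figures describe the stopping rule only and do not convert into a shift in ICF.

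**The case against.** The strongest reply is that the ICF link runs through Section 5.2 alone. Only that section sets the conditioning stimulus, it does so from a resting threshold that it defines itself, and the paired-pulse item of Appendix B never refers back to item 12. Item 12f gives a reason that concerns the CSP only, and 12g goes on to CSP measurement, so 12f looks like a CSP instruction under a shared heading. Item 12d is poorly worded and can be read as a descending search that brackets the 5-of-10 point; the figure of 4 responses is an inference from 6 failures. The measurements are made in one laboratory, with procedures said to have been published, and staff may already use one method throughout.

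Much of this stands. The CSP-only reading of 12f is plausible, and the response count is the weaker half of the conflict. But the text does not say so. Motor threshold is named in the heading, 12f carries no exemption, and Section 5.2 itself points to Appendix B for detail. The relaxed-versus-contracted conflict stands without the count.

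A reader might go further and infer that participants are being placed in the wrong stratum, that ICF drifts from week to week, or that the power stated in Section 7.1 is reduced. The documents do not support this. Nothing shows that operators follow different texts. If one rule is used throughout, even an unintended one, the expected result is a common shift relative to the 1.5 cut, not random misclassification. Any loss of power would rest on an assumed misclassification rate with no connection to this conflict.

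**Conclusion.** The point holds as an inconsistency in the written procedure for the trial's stratifying measurement. It is clear on muscle state and less clear on response count. Taken literally, Appendix B produces a threshold other than the RMT from which the ICF conditioning stimulus is set.

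The size of any effect on ICF, on the share of participants above 1.5 or on the primary test cannot be derived from the documents, and no figure should be attached to it. The conclusion assumes that an operator would carry the Appendix B threshold into the ICF measurement. The cross-reference in Section 5.2 makes that a reasonable reading of the text, but it is not evidence of what the laboratory does. It would also be too strong to say that one visit's ICF governs everything: the single Phase I baseline value fixes only the stratum and the moderator, while the secondary endpoint uses weekly values and Phase II has its own baseline.

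**What to change.** Reconcile Section 5.2 and Appendix B, item 12, so that one motor-threshold definition, covering both muscle state and response count, is used for ICF at every visit in both phases. One way is to state that 12f applies to the cortical silent period only and to align the count in 12d with Section 5.2. If Section 5.2 does not describe the laboratory's method, correct Section 5.2 instead.

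The cost is about two lines of protocol text. No new data and no change to the analysis are needed.
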